**ii. Description of American Shoulder and Elbow Surgeons Score (ASES)**

The ASES form was created by the Society of the American Shoulder and Elbow Surgeons to help standardize outcome measures by both combining a physician-rated and patient rated section. The total maximum score (and best outcome) is 100. Half of the score is weighted for pain and the other half for function. The final pain score is calculated by subtracting the visual analog scale from 10 and multiplying by 5. For the functional portion, each of the 10 separate questions are on a scale from 0 to 3. The functional portion total is then multiplied by 5/3 to make it a total of 50 points. In summary, 50 points come from the visual analog scale and the other 50 come from the functional portion, which equals a possible total of 100.

1. What is your usual work/occupation?
2. Usual sport/leisure activity?
3. Do you have pain at night? Y/N
4. Do you take pain killers such as paracetamol (acetaminophen), diclofenac, or ibuprofen? Y/N
5. Do you take strong pain killers such as codeine, tramadol, or morphine? Y/N
6. How many pills do you take on an average day? Quantity
7. Intensity of pain? 0 to 10 (10 being the worst)
8. Is it difficult to put on a coat? Unable to do, very difficult to do, somewhat difficult, not difficult
9. Is it difficult for you to sleep on the affected side? Unable to do, very difficult to do, somewhat difficult, not difficult
10. Is it difficult for you to wash your back/do up bra? Unable to do, very difficult to do, somewhat difficult, not difficult
11. Is it difficult for you to manage toileting? Unable to do, very difficult to do, somewhat difficult, not difficult
12. Is it difficult for you to comb your hair? Unable to do, very difficult to do, somewhat difficult, not difficult
13. Is it difficult for you to reach a high shelf? Unable to do, very difficult to do, somewhat difficult, not difficult

14. Is it difficult for you to lift 10 pounds above your shoulder? Unable to do, very difficult to do, somewhat difficult, not difficult
15. Is it difficult for you to throw a ball overhand? Unable to do, very difficult to do, somewhat difficult, not difficult
16. Is it difficult for you to do your usual work? Unable to do, very difficult to do, somewhat difficult, not difficult
17. Is it difficult for you to do your usual sport/leisure activity? Unable to do, very difficult to do, somewhat difficult, not difficult

iii. Provide a schedule of all study assessments and subject activities, including a tabular representation or timeline as applicable -

## VI. Safety Monitoring Plan

### a. Definition of adverse events, serious adverse events

- i. All surgical interventions are accompanied by a risk of blood loss, infection, and damage to surrounding structures. Patients will be advised that post-op pain and stiffness is expected and normal. If this surgery is not successful, there may be need for additional surgeries. If the patient undergoes rotator cuff repair in addition to biceps tenotomy and tenodesis, there are risks that the rotator cuff repairs may fail to heal or even retear. Symptomatic retears may require further operative intervention. Scar tissue accumulation may also require further operations. All of these risks are routine risks associated with arthroscopic biceps tenotomy and

tenodesis with or without rotator cuff repair. The only known possible risk specific to this research study will be an additional 1-2 minutes under anesthesia for those selected for the intervention group. This risk is considered low with minimal risk to the patient. There is minimal risk of loss of patient confidentiality. All data will be recorded and stored in the password protected Loyola R: drive, then will be de-identified prior to data analysis.

- b. What procedures will be used to monitor subject safety?
  - i. As with all patient interactions, safety will be prioritized by all participants involved in caring for the patient. Our research project does not incur any increased safety concerns. However, due to the nature of research, participants in our study will inherently receive more attention because of increased interactions with members of the research team. If any concerns, suggestions, or questions arise during our research project, they will immediately be brought to the attention of the principal investigators of the study.
- c. Who (list names) will identify, document, and report adverse events?
  - i. Adverse event identification will be the responsibility of each member of the research team, specifically, [name] and [name]. These events will be reported promptly to the IRB office.
- d. What are the stopping rules with regard to efficacy and safety?
  - i. All patients involved in the study will be allowed to withdraw at any time. Consent may be revoked at any time prior to completion of the study, which is expected to be a duration of one year. All members of the research team will be held responsible for notifying the sponsors of the study ([name] & [name]) if patient safety is compromised.

## **VII. Plan for patient identifiers and information**

- a. Plan to protect patient identifiers for improper use and disclosure
  - i. All patient health information (PHI), demographics and sensitive data will be kept on the Loyola provided secure server in an assigned password protected folder located on the R: drive. All paper records, if any, will be kept in a locked cabinet in the offices of the principal investigator.
- b. Removal of patient identifiers and record retention
  - i. Upon completion of the study, electronically stored patient identifiers will be deleted from the R: drive and any paper records will be disposed of using Loyola Medical Center approved shred bins for such purpose.
- c. Individuals with access to protected health information
  - i. Only research team members listed on the protocol will be granted access.
- d. Summary of the use of the data
  - i. Data will be collected in a prospective manner, statistically analyzed and formatted for presentation at regional or national surgical meetings and/or publication in peer reviewed surgical/medical journals.

### **VIII. Statistical Analysis Plan**

The primary aim of assessing change in the ASES score from baseline to post-surgery between the control and intervention groups will be assessed using a student's t-test, as indicated in the study design.

In addition, longitudinal mixed effects models will be used to estimate changes in ASES scores, over all time-points using a random effect for surgeon. Other relevant patient characteristics such as age, sex, and Charlson score will be included to explore the adjusted relationship of the intervention and outcomes over time.

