### **IV. Study Design**

- a. Experimental Design: Patients that meet the inclusion/exclusion criteria will be eligible for participation in the study. The design will be a single blinded format where the surgeon will be aware of what treatment the patient will receive (Control vs. Intervention). The patient will not be informed of what arm of treatment they were selected for. Block randomization will be utilized to place an equal number of patients into both groups.
- b. Study Population: Patients undergoing arthroscopic shoulder surgery with long head of the biceps tendon pathology.
- c. Sample size determination and power analyses:  
Based on previous studies, it is assumed that the pre-ASES score for all patients undergoing biceps tenodesis is approximately 45. At 1 year post surgery, the standard of care group will increase to 85 (Mean difference = 40, STD=18). It is hypothesized that the treatment group with anatomical fixation will increase to approximately 93 (Mean difference = 48, STD=18).

The necessary sample size was calculated using 80% power of rejecting the null hypothesis (that there is no difference in change in ASES scores between the two groups of interest), when the population mean difference in ASES is  $\Delta 1 - \Delta 2 = 48 - 40 = 8$ , with a standard deviation of 18, and with a significance level (alpha) of 0.05. This power and sample size calculation was computed using a two-sided two-sample equal-variance t-test.

To achieve this power, at least 81 patients will need to be enrolled in each group. Patients will only be randomized once to this study. If a patient has a repeat surgery, that case will not be eligible for randomization.

- d. Study outcomes/endpoints
  - i. Study endpoint will be decided based on the power analysis that was calculated by the research team biostatistician.
  - ii. Data collected:
    1. Demographics: Name, MRN, age, sex, hand dominance, ethnicity, profession, BMI

2. Clinical Factors: Indication for surgery, procedures performed, past medical history of upper extremity pathology
3. Medical History: Myocardial infarction, congestive heart failure, peripheral vascular disease, transient ischemic attack or cerebrovascular accident, dementia, chronic obstructive pulmonary disease, connective tissue disease, peptic ulcer disease, liver disease, diabetes, hemiplegia, chronic kidney disease, solid tumor, leukemia, lymphoma
4. Measurements: (in mm)

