- a. At the patient's initial clinical visit, they will be given a copy of the informed consent that details specifics of the research study that we are conducting. It will be translated into a health comprehension level deemed appropriate by the IRB committee (7th grade).

- iii. Screening procedures

1. What procedures are required for screening?

- a. At the initial outpatient office visit, qualifying patients will be further screened using the aforementioned inclusion/exclusion criteria. At that time, [name] or [name] will speak with the patient about the research study to its entirety, which will include the potential benefits, risks and alternatives.

2. What is the screening schedule (number of visits, length of visits)?

- a. Patient will be screened during their initial outpatient office visit.
- b. Those patients that express interest will again be approached on the day of surgery. On this day, a member of the research team will explain to the patient, for the second time, the research project.

3. Which screening tests/procedures are part of standard care and which are for research purposes only?

- a. A member of the research team will be at the office visit to obtain an ASES score prior to surgery and will contact patients via phone at 2 weeks, 6 weeks, 3 months, and 6 months and one year after surgery.
  - b. Standard of Care: Aspects of the physical examination including range of motion, strength, neurovascular status, and shoulder/elbow specific testing will be recorded by the surgeon in the chart per standard history and physical documentation.
    - i. A member of the research team will gather this information via chart review.
  - c. Research Specific: On the day of surgery, a member of the research team will ask the patient a short series of questions in order to calculate an American Shoulder & Elbow Surgeon (ASES) score as their preoperative score. The member of the research team administering the questionnaire will not be blinded. A specific description of the ASES questionnaire is detailed later in the protocol. This questionnaire will again be tested at the patient's 6 month follow up.
4. What happens with screen failures (including any data gathered during screening)?
  - a. Those patients that are not eligible based on the inclusion/exclusion criteria, will not be included in the study.

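### The primary test names no visit: the sizing implies the 1-year ASES score, but two provisions point to 6 months, and one of them would obstruct the 1-year call

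*Combined protocol and SAP*

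**What the plan says.** Section VIII defines the primary comparison as "The primary aim of assessing change in the ASES score from baseline to post-surgery between the control and intervention groups", assessed by a t-test with a reference back to the study design. The abstract describes the same comparison. Neither names a visit.

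Sections V.a.iii.3.a and V.e.i both state that the research team "will contact patients via phone at 2 weeks, 6 weeks, 3 months, and 6 months and one year after surgery", so five scores qualify as post-surgical.

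The other relevant places are:

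- **Section IV.c (sizing).** "At 1 year post surgery, the standard of care group will increase to 85", from about 45 at baseline. The anatomic-tension group is assumed to reach about 93.
- **Section IV.d.i (endpoint).** It says the endpoint will follow from the power analysis and gives no time.
- **Section V.a.iii.3.c (research-specific procedures).** After describing the pre-operative questionnaire it adds: "This questionnaire will again be tested at the patient's 6 month follow up". It mentions no other re-test.
- **Section V.e.i.2 (assessments).** All identifiable data for a patient are deleted from the research records once the 6-month appointment is done.
- **Section VII.b (identifiers).** Electronic identifiers are deleted when the study is complete.
- **Section VI.d (stopping rules).** The study is expected to last one year.

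**The concern.** A primary endpoint needs a variable, a summary and a time. Here the time has to be inferred, and the provisions from which a reader would infer it do not agree. Two things are at stake.

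First, the power statement belongs to one visit. If the primary result were read at 6 months, it would test a difference about which the plan assumes nothing.

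Second, when the visit is not fixed in advance, it can be settled after results are known. The nominal 5% error rate then no longer holds.

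There is also a practical problem. Under section V.e.i.2 as written, the team would no longer hold the identifiers needed to phone a patient at one year and link the answer to the baseline score. Following the protocol to the letter could therefore leave 6 months as the last usable score, whatever was intended.

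**Working it through.** **1. Reproduce the plan's figure.** The inputs are all from section IV.c: changes of 48 and 40 (difference 8), SD 18, alpha 0.05, 80% power, and a calculation "computed using a two-sided two-sample equal-variance t-test".

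Normal approximation, per group:
n = 2 × (1.960 + 0.842)² × 18² / 8² = 2 × 7.849 × 324 / 64 = 79.5, rounded up to 80.

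The exact two-sample t-test (noncentral t) needs 80.44, rounded up to 81, with power 80.3% at 81 per group. The stated 81 is reproduced. Its only effect assumption is the 8-point difference at 1 year.

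**2. Power at another visit.** The documents give no 6-month means or SD, so only assumed values can be shown. With 81 per group and the same t-test:

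| Assumed difference | Assumed SD | Power |
|---|---|---|
| 8 | 16 | 88.5% |
| 8 | 18 | 80.3% (the plan's 1-year case) |
| 7 | 18 | 69% |
| 6 | 18 | 56% |
| 5 | 18 | 42% |
| 8 | 20 | 72% |
| 8 | 22 | 63% |

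Power at 6 months could be higher or lower than 80%. The plan does not say which.

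**3. False-positive rate if the visit is chosen late.** Suppose there is no true effect, both the 6-month and the 1-year tests are run, and either may be called primary. Let Z1 and Z2 be the two test statistics, approximately standard normal with correlation r. The documents do not give r, so it is assumed.

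Counting either direction: rate = 1 − P(|Z1| < 1.96 and |Z2| < 1.96).
Counting only results that favour the intervention: rate = 1 − P(Z1 < 1.96 and Z2 < 1.96).

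| r (assumed) | Either direction (nominal 5%) | Favouring intervention (nominal 2.5%) |
|---|---|---|
| 0.5 | 9.1% | 4.5% |
| 0.7 | 8.3% | 4.2% |
| 0.8 | 7.8% | 3.9% |

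These are upper bounds. They apply only if both tests are examined and the better one is always reported as primary.

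**4. Set the provisions against each other.**

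| Provision | Visit it supports |
|---|---|
| IV.c sizing | 1 year |
| IV.d.i endpoint, through the power analysis | 1 year, indirectly |
| VIII reference to the study design | 1 year, indirectly |
| V.a.iii.3.a and V.e.i contact schedule | 1 year is collected, and so is 6 months |
| VI.d expected duration | 1 year |
| V.a.iii.3.c re-test | 6 months |
| V.e.i.2 deletion of identifiers | 6 months as the last linked contact |
| VII.b deletion of identifiers | end of study, compatible with 1 year |

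The balance favours 1 year. V.e.i.2 cannot easily be carried out together with the one-year call, and its timing differs from that in VII.b.

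**The case against.** The strongest reply is that the intended visit is plain enough. Section VIII refers to the study design, section IV carries that heading, and the only post-operative time in it is 1 year. Section IV.d.i ties the endpoint to the same calculation, a one-year ASES call is scheduled twice, and the study is expected to last a year. Most of this stands, and 1 year is the likeliest intention. But it remains an inference: the reference in section VIII is attached to the t-test, and IV.d.i defers the endpoint without stating it.

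Three stronger readings are tempting, and the documents do not support them.

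- **That V.a.iii.3.c flatly contradicts a 1-year endpoint.** It sits under screening procedures, calls 6 months neither primary nor the only re-test, and names a visit that is already among the five contacts. It is better read as incomplete.
- **That any of the five visits could become primary.** This would give about 13-18% under the same assumed correlations. No provision links the 2-week, 6-week or 3-month score to the primary aim, and section VIII already uses all time-points in the additional mixed model. Only the choice between 6 months and 1 year has support in the text.
- **That a 6-month readout would be underpowered.** With no 6-month means or SD, neither the direction nor the size of any loss can be stated.

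**Conclusion.** The point holds as a gap in the definition of the primary endpoint, made worse by two 6-month provisions. The sample size is not in error: 81 per group is reproduced, with 80.3% power for an 8-point difference at 1 year and SD 18. That power does not carry over to 6 months, where it is unknown.

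A choice between the two visits made after seeing results would raise the two-sided error rate from 5% to about 8-9%, or from 2.5% to about 4-4.5% for results that favour the intervention. Both ranges assume a correlation of 0.5 to 0.8 and are ceilings. A reader might infer that the plan intends such a choice. Nothing in the documents says so; the plan only fails to rule it out.

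The most concrete defect is the deletion of identifiers after the 6-month appointment, because carrying it out as written would obstruct collection of the outcome on which the sizing rests. The correction should be made, but the finding does not undermine the design.

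**What to change.** - In the abstract, section IV.d.i and section VIII, state that the primary endpoint is the change in ASES from baseline to 1 year after surgery, compared by the t-test already planned.
- Rewrite the re-test sentence in V.a.iii.3.c so that it matches the five-contact schedule in V.a.iii.3.a.
- Move the deletion of identifiers in V.e.i.2 to after the 1-year contact, consistent with VII.b. Without this change, naming 1 year would not secure the endpoint.
- Label the 2-week to 6-month comparisons, which the mixed model already covers, as secondary.

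The cost is wording only: the number of patients and the contact schedule do not change. The sponsor gives up a 6-month primary readout and holds identifiers for about six months longer per patient. The text on data protection should say so.

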14. The tendon is shortened
15. The sutures from the biceps are passed through the Arthrex cortical button
16. The pectoralis major tendon is retracted and 2 centimeters proximal to the distal insertion a unicortical bone tunnel is drilled in the bicipital groove with a 3.2 millimeter drill
17. The wound is irrigated and the biceps button is threaded into this tunnel and then flipped. The suture is tensioned, securing the biceps against the groove
18. The skin is closed in the usual fashion

e. Study Assessments and Activities

- i. If indicated, patients will undergo biceps tenodesis, as described above
  1. Standard protocol for [name] and [name] is for patients to follow up at 2 weeks, 6 weeks, 3 months, and 6 months after surgery.
    - a. A member of the research team will be at the office visit to obtain an ASES score prior to surgery and will contact patients via phone at 2 weeks, 6 weeks, 3 months, and 6 months and one year after surgery.

- b. A member of the research team will retrospectively collect history and physical examination data using [name] or [name] notes (Complications, Range of motion, strength, special shoulder or elbow physical exam tests).
2. Once the patient has completed their 6 month follow up appointment, all identifiable data from that patient will be deleted from all research records.

[figure not shown]

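### The primary t-test on ASES change can use only patients with a 1-year score, ignores up to four earlier scores, and the additional mixed model as specified does not repair this.

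*Combined protocol and SAP*

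**What the plan says.** Section VIII makes a Student's t-test primary: "The primary aim of assessing change in the ASES score from baseline to post-surgery between the control and intervention groups will be assessed using" that test, with a reference back to the study design. It names no time point, analysis set or rule for missing scores.

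The time point has to be taken from section IV.c: "At 1 year post surgery, the standard of care group will increase to 85 (Mean difference = 40, STD=18", with a change of 48 hypothesized for the intervention group. The target is 81 per group, and no allowance for loss is mentioned.

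Section VIII adds that "longitudinal mixed effects models will be used to estimate changes in ASES scores, over all time-points", with a random effect for surgeon. No patient-level random effect or within-patient covariance is named.

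Section V.e schedules ASES phone calls at 2 weeks, 6 weeks, 3 months, 6 months and one year. The surgeons' standard schedule is "for patients to follow up at 2 weeks, 6 weeks, 3 months, and 6 months after surgery", so no routine clinic visit accompanies the 1-year call. Section V.e.i.2 has identifying data erased from the research records once a patient has attended the 6-month appointment, whereas section VII.b places erasure at the end of the study. Section V.a.iii.3.c mentions repeating the questionnaire at 6 months. Section VI.d says: "All patients involved in the study will be allowed to withdraw at any time".

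**The concern.** A change score needs both of its ends. A patient who is lost after the 6-month call has a baseline and four post-operative scores but no 1-year change, and so does not enter the primary test.

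Patients who are doing poorly may be less likely to answer. If that tendency differs by arm, the arms that remain are no longer comparable, and the error can go either way. The earlier scores show how the lost patients were doing, and the t-test cannot use them. A reader might expect the mixed model to pick this up. As specified it does not link a patient's own scores to one another, and it is in any case not the primary analysis.

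**Working it through.** **Inputs from section IV.c:** difference 48 − 40 = 8; SD 18; two-sided alpha 0.05; 80% power; equal-variance t-test; 81 per group.

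**Assumed, because the documents give no figure:** loss rates, how loss depends on the score, and the correlation ρ between 6-month and 1-year change (0.5 or 0.7).

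**1. The plan's own figure.** The normal approximation is n = 2(1.960 + 0.842)² × 18² / 8² = 79.5, so 80 per group. The exact noncentral t gives power 0.798 at 80 and 0.803 at 81. The stated 81 reproduces, with no allowance for loss.

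**2. Loss unrelated to outcome.** There is no bias. Completers per arm and t-test power are:
- 10% loss: 73 per arm, 0.760
- 15% loss: 69 per arm, 0.736
- 20% loss: 65 per arm, 0.710

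Using the 6-month score at 20% loss with ρ = 0.7, the variance is (2 × 324/81) × [(1 − 0.49)/0.8 + 0.49] = 8 × 1.1275 = 9.02. The SE is 3.00 and the power about 0.76 by normal approximation (75% in simulation).

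**3. Selective loss in one arm, by hand.** Suppose that arm keeps a fraction l of patients below the median 6-month score and h above it, while the other arm loses the same total share at random. With 0.798 = √(2/π), the mean 1-year change among that arm's completers shifts by

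ρ × 18 × 0.798 × (h − l)/(h + l).

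- l = 0.7, h = 0.9 (20% lost): 0.9 points at ρ = 0.5 and 1.3 at ρ = 0.7. Simulated type I error is about 6% to 6.5%.
- l = 0.6, h = 0.9 (25% lost): 1.4 and 2.0 points. Simulated type I error is 7.4% to 10%.

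Check on the last case: 61 completers per arm give SE = 18√(2/61) = 3.26. The shift is 2.0/3.26 = 0.62 SE, so the rejection rate is about 9.5%.

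Both arms lose the same share here, so equal loss rates do not protect.

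**4. Selective loss, simulated.** 81 per arm, ρ = 0.7, logistic loss on the observed 6-month score. The comparison is a likelihood estimate that uses the 6-month scores.

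| Scenario | Completers' t-test | Using 6-month scores |
|---|---|---|
| True 8; dependence in controls only, 24% lost | 5.4, power 39% | 8.0, power 73% |
| Same pattern, 14% lost | 6.4, power 56% | 8.0, power 77% |
| True 8; dependence in intervention arm only | 9.95 | 7.9 |
| True 8; same dependence in both arms, 22% lost | 7.4, power 65% | 8.0, power 74% |
| True 0; dependence in controls only | type I error 12% | type I error 5% |

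A run with dependence stronger in controls at about 24% loss gave 5.2.

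**5. The planned mixed model.** In the 25% scenario of step 3, with no true effect (150 runs, correlation 0.7), a model with only a surgeon random effect had bias 2.11, against 2.13 for the t-test. Adding a patient random effect reduced it to 0.09 (simulation SE 0.24). The surgeon-only fits gave convergence warnings, as expected when the simulated surgeon variance is zero. The result has a simple explanation: with arm-by-visit means and no patient-level link, the 1-year contrast is just the difference in observed 1-year means.

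**6. Loss driven by the unseen 1-year score.** With dependence in one arm only and 24% loss, bias was −3.7 for the t-test and −2.0 for the likelihood estimate. The earlier scores then remove only part of it.

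**The case against.** **Exclusion is inferred.** No complete-case rule is written, and a reader should not report that the plan orders patients to be dropped. What stands is that nothing supplies a missing 1-year value, so the test as written cannot use those patients.

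**The 1-year endpoint is also inferred.** It comes from the power section, while section V.a.iii.3.c points to 6 months. If 6 months were primary, the same gap would remain with up to three earlier scores.

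**A reader might infer that the planned mixed model already handles this and only needs promoting.** Section VIII does not support that. Only surgeon is named, and the within-patient term that does the correcting would be new.

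**A reader might infer that section VI.d permits only complete withdrawal.** That is not established. The section does not say that earlier scores are discarded or later calls refused, and the consent pages, which may carry such terms, are not available.

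**The bias is conditional.** Patients are blinded, which makes arm-specific loss less likely. With equal dependence in both arms and no true effect, type I error was 4.5%. With logistic slopes of 1 against 0.5 per SD at 23% loss it was 6.5%. The 12% needs a stronger contrast. This objection stands and limits the claim, although equal dependence still shrank a true 8 to 7.4.

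**Much of the lost power comes from sizing without an allowance for loss.** That is true, and a separate matter. The model recovers only about four percentage points under random loss.

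**Conclusion.** The concern holds in this conditional form. As written, the primary test can use only patients with a 1-year score, and no other planned analysis makes proper use of what is known about the rest.

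With ρ = 0.7 and 14% to 24% loss that depends on earlier scores more strongly in controls, a true difference of 8 is estimated at about 5.2 to 6.5. With no true difference, arm-differential dependence gives type I error of about 6% to 12%. If the dependence lies in the intervention arm, the estimate is too favourable. If loss is unrelated to outcome, only power suffers: about 71% against 75% at 20% loss. The loss rates, the form of dependence and ρ are all assumptions.

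A reader might go further and infer that most 1-year scores will be lost, because identifiers are erased after 6 months. The passages conflict on when erasure happens, so they do not establish that. They do make missing 1-year scores more likely unless they are reconciled.

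**What to change.** In section VIII:
- Name 1 year as the primary time point, and reconcile this with the 6-month questionnaire in section V.a.iii.3.c.
- Take as the primary estimate the 1-year arm difference from a repeated-measures model fitted to all randomized patients with any post-operative score. Include visit as categories, arm by visit, baseline ASES and surgeon, and add an unstructured within-patient covariance or a patient random effect.
- Keep the completers' t-test as supportive.
- Add a sensitivity analysis for loss that depends on unobserved scores.

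In section V.e.i.2, reconcile the erasure of identifiers after the 6-month appointment with the 1-year call and with section VII.b, so that the 1-year score can be obtained and linked to the earlier ones.

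The cost is protocol and SAP wording; every score used is already scheduled. The price is reliance on missing-at-random given the earlier scores. That is a weaker assumption than the completers' t-test needs, and the sensitivity analysis would probe it.
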